The Principal Investigator will screen potential subjects based on the inclusion and exclusion criteria. Potential subjects will have met the clinical criteria to be treated with BoNT therapy prior to screening for the study.

Informed Consent Process

Clinical visits will occur at Wichita Women's Pelvic Surgery Center at Associates in Women's Health (WWPSC) in Wichita, KS. Investigators and research staff will be available to answer patient questions at the time of the informed consent interview. The consenting process will take place after patient in-processing according to standard clinic operating protocols, and after the patient has satisfied the clinical criteria and has elected to undergo BoNT injection therapy with the Principal Investigator.

After electing to undergo the injection therapy, the Principal Investigator will review the eligibility criteria to determine if the patient is eligible to participate in the study. If all inclusion criteria are met, the Principal Investigator or a member of the research team will present the informed consent form to the patient and will discuss the study with the potential subject. The patient will be informed that participation is voluntary, and their decision to participate will not affect their medical treatment or procedures related to the BoNT injection therapy. Consent will only be sought from those patients that meet fulfill the study inclusion criteria. All materials will be provided to the patient and the conversation will take place in English (Appendix A – ROBIN Consent Form).

After all questions have been answered, and the patient has had adequate time to review the informed consent form, if the patient would like to participate, the research team will ask the participant to sign the consent form. If the patient would like additional time to review the informed consent form and to consider participation, the patient can either schedule a visit to complete the form before their visit, or can sign the informed consent form when they check in for their procedure.

A copy of the signed consent will be provided to the participant. The Principal Investigator will be notified that the patient consents to participate in the study. After consenting, the investigators and research assistant will review all materials for completeness before the subject leaves the clinic site.

If consent to participate in the study is not given, no information collected during the visit will be used in the study. Instead, the information will be used for normal documentation of patient care.

Patients will be consenting to data collection and to research participation to receive an intervention or a placebo above and beyond standard clinical practice.

Alternatives to Participation

The alternative to participating in this study would be to not participate in the study. The patient will still undergo the BoNT therapy as anticipated. Even if the patient declines to participate in the study, the patient would still receive the B&O suppository as the Principal Investigator's standard of care, or patients can notify the clinician they do not want to utilize a suppository.

Costs to Subjects

The study subject will be responsible for costs associated with the BoNT injection therapy, and standard medical costs associated with their treatment. In the instance that the insurance company will not pay for the injection therapy or the associated standard of care procedures, the subject will be notified, and the subject will be responsible for the costs associated with their medical treatment. If the subject does not have insurance, the subject has previously agreed to cover the costs associated with the treatment.

The only costs that the subject will not be responsible for are those related to the study procedures. The subject is not required to cover the cost of the suppository, or the pain assessment forms.

New Study-Related Information

Although investigators do not anticipate developments in research or information related to the study, the study subject will receive new information from investigators via letter correspondence. Any correspondence will be disseminated by the Principal Investigator, and the data coordinator will track and monitor that each study subject receives the information.

Participation Incentive

Subjects will receive a \$25 gift card at the conclusion of the 2-week follow-up appointment to assist with travel/driver costs. If the subject withdraws before the 2-week follow-up, the participant will not receive an incentive for participation.

Research-Related Injury

If the study subject were to be injured as a result of study procedures (separate from the BoNT therapy), subjects will be advised to immediately contact the Principal Investigator, [name] [REDACTED] [name] will decide what type of treatment, if any, is best for the study participant at that time.

Data Collection and Protection

Data Collection Procedures

Data collection will occur after obtaining informed consent for the patient to participate in the study. Demographic data will be collected to include clinical, surgical, functional, post-procedure, charted data collected as part of routine clinical visit and standard of care (Table 4). Data will be collected on a paper form (Appendix B – Data Collection Form). Follow-up data will include newly charted clinical and functional data.

Table 4. Summary of Participant Demographic Data Collected
Date of 1st consultation
Height
Weight
Body Mass Index
Race/Ethnicity
Smoking status
Menopausal status
Diagnoses
Prior surgeries
Past medical history
Medications
Indication for BoNT injection procedure

The day of the procedure, the participant will check in at the front desk. A nurse will escort the participant back to the procedure room for preparation. The participant will be given a pain assessment form with a numeric rating scale that will ask the participant to evaluate their bladder pain prior to standard analgesia and the procedure (Appendix C – Pain Assessment Form - Po). After completing the assessment, the participant will be positioned for the procedure and will be administered standard analgesia plus active or placebo suppository (based on randomization assignment).

Aside from suppository placement, BoNT injection protocols that are in compliance with best practices established by Allergan® and the FDA will be followed. In summary, BoNT will be reconstituted in 10ml normal saline and injected in 1/2ml increments (20 injections). Standard analgesia consists of bladder instillation with 50-60ml of 1% lidocaine solution with 10ml of sodium bicarbonate. Instillation is maintained for 40 minutes prior to the procedure. During that time, the patient will rotate while on procedure table (10 minutes on supine, 10 minutes prone, 10 on each side) to maximize bladder wall contact with anesthetic. The patient will then be placed in lithotomy position for cystoscopic injection of BoNT. A 17 french 30 degree cystoscope will be used. Injection will be carried out using a flexible botox injection needle designed for the procedure. All patients will undergo standard screening for preoperative UTI and antibiotic prophylaxis per accepted guidelines.

After 40 minutes of receiving the analgesic and suppository, and right before the procedure, the participant will be asked to report their bladder pain using a numeric rating scale (Appendix D – Pain Assessment Form – Pa-P20).

Patients will undergo 20 total injections at time of BoNT treatment. An investigator will perform pain assessments during the procedure. During the procedure, the participant will be asked their bladder pain using the numeric rating scale after the first 10 of 20 injections performed during the procedure and after the next 10 of 20 performed during the procedure (Appendix D – Pain Assessment Form – Pa-P20).

After the procedure is completed, the participant will be asked to complete a voiding trial, and will be given a pain assessment form, answering a Likert scale question regarding their satisfaction with their pain management during the procedure (Appendix E – Pain Assessment Form - Post BoNT). After the voiding trial is completed and the Principal Investigator has provided standard medical counseling and care after the procedure, the participant is released from the clinic.

Patient pain outcomes will be measured using numeric rating scales (NRS) and satisfaction with pain management during the procedure. The Principal Investigator will perform the clinical evaluation and in-office procedures associated with this study. The investigators will assist with the pain assessments. Patient information will be collected as part of the normal course of care associated with routine post-surgical visit and will be charted according to routine clinical practice. Pain assessments will be collected for research purposes.

Description of Follow-Up

During the informed consent process, subjects will agree to a standard of care follow-up with the Principal Investigator, two weeks after their in-office procedure where they will undergo PVR assessment. The Principal Investigator will perform a clinical exam as part of their standard of care. Adverse and serious effects will be assessed during follow-up. Both the results of the PVR assessment, adverse and serious effects, and result of urine culture will be documented (Appendix F – Assessment Form – 2-Week Follow-up).

Cessation Rules/Termination of Study

During the consenting process, subjects will be advised that they may voluntarily withdraw from this study at any time. They will not be obligated to reveal their reason for withdrawal. Additional circumstances for which a subject may not continue study participation include death, or lost to follow-up status. A subject will also be withdrawn from the study if their procedure was not performed at Associates in Women's Health. Moreover, a subject will be withdrawn from the study if the subject does not follow the study requirements. The Principal Investigator has discretion in removing a patient from the study if study requirements are not met.

Subjects terminated from the study will undergo standard treatment of care. All data collected during the study prior to cessation will be kept on hold at the discretion of the

investigator(s) and research assistant, unless the subject cancels the permission for researchers to use the collected data.

To withdrawal from the study, the subject will need to write a statement to the Principal Investigator. The mailing address to withdraw is: [name], KU School of Medicine- Wichita, Department of Obstetrics and Gynecology, [REDACTED]
[REDACTED]

Once a written statement has been received, the researchers will remove the subject from the current list of subjects and will be placed on the withdrawn list. Information that had already been collected from the patient will be kept. Subjects will continue to receive standard treatment of care; however, all data collected after receiving the study withdrawal statement will not be added to the cumulative study data.

Human Subjects Protections

Researchers involved with this study will have Human Subjects and HIPAA Certification. This proposal will be submitted to two IRBs; the Wichita Medical Research and Education Foundation IRB and the University of Kansas School of Medicine – Wichita Human Subjects Committee 2 IRB. This study will not commence until final approval is received from the IRBs.

Methods to Minimize Risks

To minimize the risks associated with this study, the privacy of potential subjects will be maintained as all Protected Health Information (PHI) will be protected and have limited access. Subject names and clinic record numbers will be maintained on a master list linked to a unique, assigned identification code generated independent of the medical record number. Much of the information we are seeking to collect is routinely collected and placed in the patient clinic and surgery charts. Access to PHI is necessary to connect patient surveys and assessments to information collected from the electronic medical record.

The master list will be maintained under secure conditions at all times. The master list will be stored at the University of Kansas School of Medicine - Wichita, Department of Obstetrics and Gynecology [REDACTED]

[REDACTED] Electronic copies of the master list will be password-protected and stored on encrypted computers/laptops. Only the data coordinator will have access to the master list in the department. The master list will be destroyed once all data has been deemed complete and analyzed, and it is determined that the master list is no longer necessary.

Only the listed investigators and their designated staff will have access to the master list and study data. The Institutional Review Boards, US Department of Health and Human Service, the Office of Human Research Protections, and other government and regulatory bodies, as required by law, may have access to this research data.

Research assistants enlisted to assist with this study will be closely supervised by the Principal Investigator. Those involved in direct patient care responsibilities, and assisting clinicians are located at Associates in Women's Health, and will not perform activities beyond their scope of care or expertise. Information technology protections and firewalls that are in place at this facility will protect the electronic data stored.

Data Security

Paper forms will be maintained under secure conditions at all times. The paper forms used in this study will not have participant protected health information listed, and will be kept in a locked office at all times. Data forms will be kept confidential during the conduct of this study. Research materials, such as protocols, IRB documents, participant information and data forms (after completion of data collection and analysis) will be kept in locked file cabinets in the University of Kansas School of Medicine – Wichita, Department of Obstetrics and Gynecology [REDACTED]

Documents and study related materials will be maintained under lock and key. Electronic files will be password-protected and encrypted, and will only be accessed by researchers listed on this study. Portable data devices (flash drives) will be encrypted and password-protected and will be maintained in secure locations in locked offices (either a co-investigator's office or the research assistant's office). At the conclusion of the study, all study related materials will be kept in locked file cabinets. Electronic files will have multiple firewalls and passwords to help keep information confidential. Electronic databases will be kept based on the record retention guidelines previously stated, and will be stored on password-protected and encrypted hard drives.

Information collected from paper forms will be entered into a computerized data file, and the file will be password protected and encrypted. Passwords will be subject to scheduled changes. The master list will be kept separately from the data collection forms. Access to study databases is restricted to an as needed basis to identified investigators and will be protected by appropriate firewalls. The database will be password-protected and encrypted. Files sent by email will first be password-protected and the email will be encrypted and sent via secure email.

Study Monitoring

The research staff will provide oversight, supervision, and monitoring of the data collection and will insure the integrity of the data which will ultimately ensure subject confidentiality. The study sites will be either the Principal Investigator's local clinic practice site, or those affiliated with the study personnel at the University of Kansas School of Medicine – Wichita.

Secure and Maintain IRB Approval at All Sites:

The Wichita Medical Research and Education Foundation IRB, in conjunction with the University of Kansas School of Medicine – Wichita Human Subjects Committee 2 IRB, will serve as the IRBs of record for this study, to include all the study locations listed previously. All protocol deviations, amendments, revisions, and continuing review

reports will be promptly compiled by the project coordinator, reviewed by the principal investigator and co-investigators, and provided to the IRBs. All research within the scope of this project will be conducted under IRB policies and guidelines.

Obtain IRB Approvals Prior to Implementing Changes to Protocol:

Investigators wish to assure the IRBs that any amendments to the protocol or supporting documents will be submitted for approval prior to implementation; problems associated with the research will be reported in accordance with IRBs policies.

Ensure general coordination of study conduct:

The principal investigator agrees to accept responsibility for the scientific conduct of this study and for the rights and welfare of human subjects. General oversight of the coordination of this study will be provided by the principal investigator, sub-investigators, and project coordinator.

Modifications to Study Protocol and Oversight:

Each review will consider whether or not the study should continue without change, be modified, or be terminated. Recommendations regarding modification of the design and conduct of the study might include:

1. Modification of the study protocol based upon review of the safety data;
2. Optional approaches when the incidence of primary study outcomes is substantially less than expected such as recommendations to extend study site; and
3. Corrective actions regarding the study site.

Any modifications to the study protocol will be submitted to the IRBs for approval prior to implementation of the changes.

To monitor adverse events or other unanticipated problems:

In lieu of a DSMB, investigators will serve in this capacity, in which they will be responsible for the following:

1. Interim/cumulative data for evidence of study-related adverse events;
2. Interim/cumulative data for evidence of efficacy when appropriate;
3. Performance of the study site;
4. Adequacy of compliance with goals for subject selection; and
5. Factors external to the study such as scientific or therapeutic developments that may impact participant safety or the ethics of the study.

The Principal Investigator and project coordinator will assume responsibility for:

1. Data quality, completeness, and timeliness;
2. Completeness of survey instruments;
3. Adherence to the protocol; and
4. Factors that might affect the study outcome or compromise the confidentiality of the trial data (such as protocol deviations).

Moreover, assessments for participant safety, study conduct and progress, and efficacy will be done. Periodic reviews of the same factors will be carried out. Each review will

consider whether or not the study should continue without change, be modified, or be terminated. Steps to unmask participants will be used to ensure participant safety if needed.

Investigator's Ethical and Regulatory Responsibilities:

Protocol adherence is the primary responsibility of the Principal Investigator. The co-investigators, and project coordinator will serve to support protocol adherence efforts and maintain an understanding of all protocol details. The principal investigator will consult with the other investigators regarding protocol revisions and amendments before adopting such changes. The IRBs will be notified of any problems during the conduct of this study.

Adverse Event Assessment and Reporting

The study team will be reviewing and assessing subject safety and data on a monthly basis. Participant pain assessments and clinical outcomes will be regularly reviewed to monitor patient safety. The Clavien-Dindo classification system will be used to monitor for adverse events and complications [33]. Adverse events specifically related to BoNT injection will also be monitored to include urinary tract infection and gastroparesis [31].

In the case an adverse event were to occur, the study investigator(s) will assume responsibility for reporting and documenting any complications. All serious events and adverse effects will be recorded on the participant's case record forms. In addition, all serious adverse and unanticipated adverse effects will be reported to the Institutional Review Boards by telephone, or in writing, within five (5) business days after the investigators first learn of the event by either the investigator(s) or the project coordinator.

The investigators are required to document all general medical complications, including, but not limited to the following: date of occurrence, date diagnosed, type of complication, and treatment. The investigator(s) and research assistant are responsible for complying with any reporting requirement of the reviewing IRBs.

Adverse events will be assessed after the suppository has been used, during the procedure, and during the voiding trial. During the two week follow-up visit, adverse events will also be assessed. The investigators do not believe there will be a need to stop or alter the study, but will stop the study if requested by the Institutional Review Board.

Record Retention

All study related documents (research materials such as protocols, IRB documents, participant information and data forms after completion of data collection and analysis) will be retained for fifteen (15) years from the date of initial IRB approval, and will be kept in locked cabinets located at the University of Kansas School of Medicine – Wichita Department of Obstetrics and Gynecology, [REDACTED]

[REDACTED]. At the time of document

disposal, documents will be shredded according to KUMC Research Institute Record Retention guidelines.

Dissemination of Results

Once the research is completed, it will be submitted to gynecologic journals and conferences, particularly those specializing in urogynecology.

Project Timeline

The project seeks to obtain Institutional Review Board approval from the IRBs by September 2015 (Table 5). This research project is anticipated to be completed by April 2017. The investigators anticipate conducting preliminary analysis after one year, and will complete continuing review forms as needed to complete the study.

Table 5. ROBIN Trial Project Timeline													
PROJECT LAUNCH Project Deliverables (X)	Academic Year 2015 - 2016												
	7	8	9	10	11	12	1	2	3	4	5	6	7
	J	A	S	O	N	D	J	F	M	A	M	J	J
Assemble project staff, create study protocol, submit for IRB approval and study funding													
Submit project for IRB approval and funding													
Receive IRB Approval			X										
Train study team and support staff													
Recruit patients from local providers offices													
Enroll patients and collect data													
Team meetings to discuss research plan, data quality, and progress on objectives													
Conduct preliminary analysis													
Review findings with team													
IRB Continuing Review													
	Academic Year 2016 - 2017												
Finalize data analysis and conclusions													
Draft abstract and submit to regional/national conferences		X											
Disseminate preliminary findings at regional/national conferences				X						X			
Draft manuscript													
Submit manuscript for publication							X						

Budget and Justification

Investigators will be requesting funding to cover costs related to the study and registration for the Principal Investigator and the Resident Investigator to present the findings of this study at the 2016 American Urogynecologic Society Annual Meeting. A detailed budget is provided below.

Personnel Costs: **\$0.00**
[name], MD, Principal Investigator (PI), will be responsible for managing and providing direction on all aspects of the project, ensuring that the budget and timetable targets are met, and providing direction to the other research personnel. Specifically he will facilitate communication between members of study team, and oversee conduct of the study, ensure all requirements for the Institutional Review Board are met, and contribute to reports, and dissemination. [name] will be performing the clinical procedures associated with this study, perform the data analysis and create reports, and disseminate results at national meetings.

[name], PGY-3, Co-investigator, will be responsible for managing and providing direction on all aspects of the project, ensuring that the budget and timetable targets are met, support Institutional Review Board approval/revisions, and providing direction to the other research personnel. Specifically she will facilitate communication between members of study team, and oversee conduct of the study personnel, perform study procedures, assist with data analysis, and create reports, and dissemination at national meetings.

[name] Study Personnel, will be responsible for facilitating team communication, coordinating protocol implementation logistics at the study site, and drafting/submitting Institutional Review Board reports and summaries, support Institutional Review Board approval/revisions, assist with team coordination, assist with data cleaning, assist with data analysis, review reports and submit abstracts for conference presentations.

Fringe Benefits: **\$0.00**
None requested.

Equipment: **\$0.00**
None requested.

Supplies: **\$1825.00**
Based on the quote provided by the compounding pharmacy, compounded belladonna and morphine pills will cost \$15.00 per pill the placebo pills will cost \$10.00. Thus, 20 compounded belladonna and morphine pills will cost \$300.00 and 20 placebo pills will cost \$200.00. Extra suppositories will be created to send for third-party validity testing and in the case where a suppository is deemed defective or dropped. Third-party validity testing will cost approximately \$500.00 Participants will receive a \$25 Walmart gift card from Walmart for participating. The total cost for incentives for 26 participants will be \$650.00. Paper supplies for surveys and printing will cost \$100.00. The poster

will be a 4x3 poster board used during presentations, which will cost \$75.00. Total costs for supplies will be \$1825.00.

Other Expenses: \$900.00

Registration to the 2016 American Urogynecologic Society Annual Meeting will be approximately \$450.00 for each attendee. The Principal Investigator and the resident co-investigator will attend to present the findings from this study. The total cost of registration to the meeting will be \$900.00.

Subcontractor Costs: \$0.00

None requested.

Personnel Costs	\$0.00
Fringe Benefits	\$0.00
Equipment	\$0.00
Supplies	\$1825.00
Other Expenses	\$900.00
Subcontractor Costs	\$0.00
Total Projected Study Costs:	\$2725.00

Appendices

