However, investigators believe that there are risks associated with this study. Physical risks associated with participating in this study, and related to study procedures include drowsiness/nausea associated with the B&O suppository if the participant is randomized to the active group. As standard of care after the BoNT procedure, patients are required to have a driver, and are advised on to operative a moving vehicle. Participants receiving the placebo may experience discomfort with the procedure, which the patient is aware of during the consent process for the BoNT therapy.

This research study involves exposure to pain and discomfort, however the risk is associated with routine clinical care since there are no established guidelines or recommendations for suppository use with analgesia during the BoNT therapy. The risk of discomfort and drowsiness/nausea associated with the study is minimal, and if the patient were to not participate in the study, would typically receive the B&O suppository as part of the Principal Investigator's routine standard of care. Researchers believe there is less than minimal risk associated with psychological, economic, social, and legal aspects of this study.

Loss of anonymity is a risk associated with research projects that involve human subjects. The research staff working on this study will take every precaution to guard patient identity in accordance with HIPPA standards. All study information and data will be grouped in aggregate and no individual information will be reported. No patient will be identified by name and protections will be in place to keep individual information confidential and anonymous.

However, risks are reasonable to the potential benefit from the study. Participation in this study will contribute to a better understanding of the treatment of bladder injection pain, which outweighs the minimal risk associated with the active group intervention. Additionally, this study may also help other patients that need to have the BoNT therapy in the future, have a better understanding of treatment options for overactive bladder, neurogenic detrusor overactivity, and refractory interstitial cystitis. Furthermore, information collected from this study would provide clinicians methods that could potentially reduce patient pain during in-office procedures, and would reduce potential healthcare costs associated with performing this type of procedure in a hospital facility.

Study Sites

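### The consent assurance that joining leaves BoNT-related treatment unaffected conflicts with the protocol's account of what decliners and placebo participants receive

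*Combined protocol and SAP*

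**What the plan says.** **Informed Consent Process.** Patients are to be told that taking part is voluntary and that "their decision to participate will not affect their medical treatment or procedures related to the BoNT injection therapy". The section ends by describing consent as covering "research participation to receive an intervention or a placebo above and beyond standard clinical practice".

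**Alternatives to Participation.** For someone who declines, "the patient would still receive the B&O suppository as the Principal Investigator's standard of care". She may opt out of it by telling the clinician.

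**Risks to Subjects.** On the placebo arm: "Participants receiving the placebo may experience discomfort with the procedure, which the patient is aware of during the consent process for the BoNT therapy". On the origin of pain: "This research study involves exposure to pain and discomfort, however the risk is associated with routine clinical care". A further sentence says "The risk of discomfort and drowsiness/nausea associated with the study is minimal" and goes on to say that a patient who did not take part "would typically receive the B&O suppository as part of the Principal Investigator's routine standard of care". The section's closing paragraph first calls the risks reasonable in general terms. It then weighs the knowledge gained against the risk of the active-group intervention.

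**Randomization** and **Research Intervention.** Allocation is with equal probability to B&O or to a suppository of inactive base. Both arms receive standard analgesia.

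**Standard of Care Procedures** and **Data Collection Procedures.** Standard analgesia is the lidocaine-bicarbonate instillation, described separately from the suppository, and it is given whether or not the patient joins.

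**The concern.** The assurance and the description of alternatives cannot both be taken at face value. If decliners normally get B&O and half of participants get an inactive suppository, the decision to join can change what a patient receives for pain before her injections. Staff who follow the consent section literally would be telling her otherwise.

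The risk section does not repair this. It traces pain to routine care, but routine care at this clinic typically includes B&O. Any extra pain from having an inactive suppository instead would come from randomization.

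At stake is informed choice about an analgesic adjunct for a painful procedure. The loss is foreseeable on the protocol's own account. The introductory text reports that providers find standard analgesia inadequate for injection pain, and Expected Results says the investigators believe the B&O arm will have less pain.

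**Working it through.** This is mainly a comparison of text, with one small count.

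**1. What each patient receives**

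| | BoNT injection | Lidocaine regimen | Suppository |
|---|---|---|---|
| Declines | yes | yes | B&O by default, unless she opts out |
| Joins, active arm | yes | yes | B&O |
| Joins, placebo arm | yes | yes | inactive base |

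Sources: Standard of Care Procedures, Research Intervention, Alternatives to Participation and Risks to Subjects. The only cell that joining can change for the worse is the suppository in the placebo arm. An assurance limited to the first two columns would be true. The assurance as written covers procedures related to the BoNT therapy without that limit, and the suppository is given 40 minutes before injection for that same procedure.

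**2. Whether the supplied text states the loss**

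- Placebo discomfort is mentioned, but as something already known from consent to BoNT itself.
- The pain risk is attributed to routine care.
- One sentence does set study discomfort beside what non-participants get. It uses the comparison to support a minimal-risk statement and does not say that placebo participants forgo the suppository.
- The general benefit-risk sentence is not limited to either arm. The specific one that follows names only the active arm.

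So the component facts are present, but the consequence of joining is not stated.

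**3. Planned size**

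The plan's figure is 13 per group, from means of 4.5 and 8, SD 3 and power 0.8 (Sample size), with two-sided alpha 0.05 (Statistical Analysis).

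- Normal approximation: n = 2 × (1.96 + 0.84)² × 3² / 3.5² ≈ 11.5, rounded up to 12.
- Two-sample t-test: 12.57, rounded up to 13, with power 0.814 at 13 per group.

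The stated 13 per group reproduces and is not in dispute.

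**4. How many are affected**

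Expected number on inactive suppository = 0.5 × 26 = 13.

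Some of these would have refused a suppository outside the trial. The documents give no refusal rate r. Taking r from 0 to 0.20 purely as an assumption, the number losing a suppository they would have had is 13 × (1 − r):

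- r = 0: 13.0
- r = 0.10: 11.7
- r = 0.20: 10.4

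**The case against.** The strongest reply is that the consent section describes much more than one sentence. A consent form is presented, the study is discussed, questions are answered and extra time is offered. Appendix A is not in the supplied copy, nor is a stretch of text between the risk and consent sections. A reader might infer that patients were misled, but the documents do not show that. This part of the objection stands, and it limits the point to the protocol wording.

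Second, the assurance can be read as an ordinary voluntariness statement about the injection, with the suppository as a separate research element. That may be the intent, and the protocol's layout gives it some support. But the same protocol calls the suppository this investigator's standard of care for the procedure, so a patient hearing the sentence would have no reason to exclude it.

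Third, an IRB can find every fact, and Risks to Subjects is not silent on placebo discomfort. This is correct, and it rules out any claim that the protocol hides the trade-off. It does not remove the conflicting assurance.

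Fourth, describing the study suppository as additional to standard practice is defensible where standard analgesia means lidocaine and the risk section notes that no guideline addresses suppository use. That stands, so rewording it is optional.

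Two further inferences go too far. The 3.5-point gap between the planning means (8 − 4.5) might be taken as the pain relief that placebo participants give up. It is a sample-size assumption, and Background says B&O has not been studied for urogynecologic office procedures. Nor do placebo participants go without standard analgesia, since lidocaine is kept for all.

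**Conclusion.** The point holds as a conflict in the protocol's wording. The assurance about BoNT-related treatment does not fit with decliners typically receiving B&O while participants have a 1-in-2 chance of an inactive suppository, and the supplied text does not state that loss as a consequence of joining. It concerns about 13 of 26 participants at most, or about 10 if one assumes that a fifth would have refused a suppository anyway. The size of any added pain is unknown.

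The conclusion rests on equal allocation, on the clinic default being as described, and on the protocol text alone. It does not question the placebo-controlled design, which can be justified while benefit is unproven. It makes no claim about what Appendix A says or what any patient was told. Correction is still worthwhile, because the sentence, followed as written, gives a misleading assurance about pain relief.

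**What to change.** 1. **Informed Consent Process.** Keep the statement that participation is voluntary, but limit the no-effect assurance to the BoNT injection and the lidocaine regimen. Add wording along these lines: *If you decline, you will be offered the B&O suppository usually given at this clinic. If you join, you have a 1-in-2 chance of an inactive suppository in its place and may have more pain during the injections.*
2. **Risks to Subjects.** List forgoing the customary suppository as a placebo-arm risk of joining, noting that its benefit here is unproven, and add it to the specific benefit-risk sentence beside the active-arm risk.
3. **Appendix A.** Confirm that the consent form says the same. If it already does, only the protocol needs to change.
4. **Optional.** At the end of the consent section, say that the study suppository takes the place of the customary one.

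The cost is an IRB wording amendment and possibly a few refusals from patients who prefer the customary suppository. Arms, visits, procedures, alpha, power and sample size are unchanged.
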